18. STATISTICAL ANALYSIS OF TRIAL RESULTS

All indicators entered into the clinical database will be listed for each patient and sorted by group (Fortelyzin® or Actilyse®), patient number and visit.

Statistical analysis was carried out using R Foundation for Statistical Computing и Graph Pad Prism 7, Graph Pad Software Inc (version 4.2). Continuous variables will be presented as mean (SD) or median (IQR). Categorical variables will be presented as n (%) and corresponding 95% Clopper-Pearson confidence intervals (CI).

Mann-Whitney U test will be used to compare continuous variables and the two-sided Fisher's exact test will be used to compare categorical variables.

Odds ratios (ORs) will be estimated and presented with 95% CIs. Outcomes will be considered as statistically significant if the p value will less than 0,05.

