8. DESIGN AND PLAN OF RESEARCH ACTIVITIES

This trial is a multicenter, open-label, randomized, parallel-group, phase III b non-inferiority trial to compare the efficacy and safety of the trial drug.

The trial will include 310 patients with massive PE. The patients will be monitored for 30 days: 1-2 days in the Intensive Care Unit and the Department of cardiology in the remaining days before discharge (on average 14 days), with an outpatient visit on the 30th day.

Start of research, initiation of centers: «_____» 20____

Enrollment of patients: «_____» 20____

Result processing and reporting: «_____» 20____

The enrollment period may be extended to total patient enrollment if a research center fails to enroll the planned number of patients. The end date of the trial is considered to be the end date of the trial in all patients involved.

In each research center, the subject of the trial is assigned a serial number that corresponds to the sequence of patient inclusion in the trial. The serial number is reflected in the CRF. The list of patient's identification is stored in the trial file. Patients are included in the trial only after signing the Informed consent form.

Before the trial, all patients will undergo the following procedures: collection of thorough medical history, signs of hemodynamic collapse, risk stratification to assess the prognosis according to the PESI classification, a physical examination, CTPA, ECG, EchoCG with the definition of PASP, ultrasound diagnostics of the inferior vena cava will be performed; blood and urine samples will be taken for laboratory tests:

- **complete blood count:** hemoglobin, red blood cells, hematocrit, leukocyte formula: neutrophils, eosinophils, basophils, monocytes, lymphocytes, platelets, ESR;
- **biochemical blood parameters:** total protein, creatinine, urea, AST, ALT, CK, NT-proBNP, total bilirubin, glucose, sodium, potassium, total cholesterol, HDL-cholesterol, triglycerides;

- **coagulogram:** fibrinogen, aPTT, INR, prothrombin, D-dimer.
- **general urine analysis:** red blood cells.

After enrollment, patients will be randomized using the «envelope method» into two equal groups of 155 patients each (a total of 310 people, including 10% who may have dropped out) and assigned to receive either Fortelyzin® or Actilyse®. Fortelyzin® will be given as single i.v. bolus over 10-15 seconds. Actilyse® will be administered following the instruction for use.

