To compare the efficacy and safety of Fortelyzin® vs Actilyse®, patients will be monitored for 3 days after administration of the drug. During this period, patients will have 6 visits (Table 5).

Table 5. FORPE trial plan

Procedure	Visit number and its period	V ₁	V ₂	V ₃	V ₄	V ₅	V ₆
		0	Day 1	Day 2	Day 7	At discharge	Day 30 (outpatient)
Inclusion and exclusion criteria		+	–	–	–	–	–
Signing informed consent form		+	–	–	–	–	–
Demographics		+	–	–	–	–	–
Anamnesis		+	–	–	–	–	–
Previous treatment		+	–	–	–	–	–
PESI risk stratification		+	–	–	–	–	–
CTPA		+	+	–	–	–	–
EchoCG with PASP definition		+	+	–	+	+	–
Ultrasound diagnostics of the inferior vena cava		+	+	–	+	–	–
Assessment of vital signs		+	+	+	+	+	+
Determining the presence of hemodynamic collapse		+	+	+	+	–	–
Physical examination		+	–	–	–	–	–
Accompanying illnesses		+	–	–	–	–	+
Changes in organs and systems		–	+	+	+	+	–
ECG		+	+	–	+	+	–
Coagulogram		+	+	–	–	–	–
General blood test		+	+	–	+	+	–
Biochemical blood test		+	–	–	–	+	–
General urine test		+	+	–	–	+	–
Fortelyzin® or Actilyse® administration		+	–	–	–	–	–
Concomitant therapy changes		–	+	+	+	+	+
Registration of AE and SAE		–	+	+	+	+	+
Assessment of bleedings		–	+	+	+	+	–

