9. TRIAL PROCEDURES

Visit 1 (Start of the trial)

Prior to administration of the trial drug, all patients will undergo the following procedures:

- determination of inclusion/non-inclusion criteria
- signing of informed consent form
- collection of demographic data (date of birth, sex, body weight)
- collection of medical history (duration of the underlying disease, previous therapy, allergological anamnesis, etc.)
- physical examination
- evaluation of changes by organs and systems
- PESI mortality stratification
- CTPA
- EchoCG
- ultrasound diagnostics of the inferior vena cava
- determining the presence of hemodynamic collapse
- ECG
- blood sampling for hematological and biochemical analyses
- coagulogram
- general urine analysis
- randomization
- Fortelyzin® or Actilyse® administration

Assignment of individual patient identification code (IPIC)

The Investigator must ensure the anonymity of the trial subjects. The full names of all patients participated in the trial are strictly confidential.

After signing the Informed Consent Form, each patient will be assigned an Individual Patient Identification Code (IPIC) in accordance with the current legislation (Table 6).

Table 6. Individual Patient Identification Code

Permission of the Ministry of Health of the Russian Federation No.	Permission's date of issue, DD/MM/YYYY/	Serial number of the medical organization specified in the Permission	Patient's initials	Patient's date of birth, DD/MM/YYYY/	A unique number assigned to the patient by the Investigator, consisting of letters and numbers (the name of the protocol and the screening number under which the patient was included in the trial)
--	---	---	--------------------	--------------------------------------	--

IPIC is established by the Insurant based on the patient data provided by the Investigator. The individual patient identification code is reported by the Insurant to the Investigator for inclusion in his medical documentation. The IPIC will be reflected in the primary documentation, CRF, and in the informed consent form. The IPIC will be transmitted by the Code Registry by the Insurant to the Insurer.

IPIC assigned to the patient is not subject to change.

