11. EFFICACY ENDPOINTS

- Primary efficacy outcome – death from any causes within 7 days;
- Secondary efficacy outcome – PASP (V1, V2, V4, V5);
- Secondary efficacy outcome – hemodynamic collapse within 7 days;
- Secondary efficacy outcome – recurrent PE within 7 days;
- Secondary efficacy outcome – death from PE within 7 days;
- Secondary efficacy outcome – death from any causes within 30 days;
- Secondary efficacy outcome – clinical composite of hemodynamic collapse within 7 days + recurrent PE within 7 days + death from any causes within 30 days.

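### PASP is compared by an unadjusted Mann-Whitney test with no planned between-arm estimate, although a pre-treatment PASP is planned in every patient

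*Combined protocol and SAP*

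**What the plan says.** Section 11 lists PASP at V1, V2, V4 and V5 as a secondary efficacy outcome. The other six efficacy outcomes, including the primary, are binary.

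V1 precedes treatment. Section 8 includes "EchoCG with the definition of PASP" among the assessments planned for all patients before the trial. Table 5 marks "EchoCG with PASP definition" at V1, V2, V4 and V5. Section 9 opens Visit 1 with "Prior to administration of the trial drug, all patients will undergo the following procedures", and EchoCG is on that list.

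Section 18 is the whole analysis plan. Continuous variables are summarised by mean with SD or median with IQR. For the comparison of arms, "Mann-Whitney U test will be used to compare continuous variables". The only between-arm estimate is in the sentence "Odds ratios (ORs) will be estimated and presented with 95% CIs", which does not apply to a pressure in mm Hg. Section 18 names no covariate, change score, repeated-measures model or deciding visit.

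**The concern.** Three things are missing for PASP.

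- **The estimate.** Section 8 describes a "non-inferiority trial to compare the efficacy and safety of the trial drug". In such a trial a Mann-Whitney p value above 0.05 does not show that PASP is similar in the two arms. That takes a between-arm difference with its confidence interval. This gap does not depend on any assumed correlation.
- **The quantity tested.** V1 is listed as part of the outcome although it comes before treatment, and the plan does not choose between raw values and change from V1. That choice alters power considerably. The trial is open-label, so it should be settled before data are seen.
- **The baseline.** V1 PASP is already planned in every patient. If it predicts later PASP, leaving it out of the comparison gives up precision.

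**Working it through.** **The plan's own figures.** There is no sample size, SD, effect size or power for PASP to reproduce. The primary-outcome calculation does reproduce: (1.960 + 0.842)² / 0.10² × (0.10 × 0.90 + 0.10 × 0.90) = 141.3 per arm, against the stated 141. The present point does not depend on it.

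**Inputs.**
- From the documents: 155 per arm (section 8) and 10% expected mortality (section 17).
- Assumed patients per arm: 140 for illustration (155 × 0.9 = 139.5); 155 as the upper limit, nearest to V2 on day 1; 126 if a further tenth is unmeasured (140 × 0.9).
- Assumed V1-to-follow-up correlation ρ: 0.2 to 0.7.
- Assumed true effect: 0.3 SD, two-sided 5% test.

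**Formulas.** Variance of the between-arm difference relative to the unadjusted comparison is 1 − ρ² for ANCOVA and 2(1 − ρ) for change from V1. The 95% CI half-width in SD units is 1.96 × √(2 × ratio / n). Example: ρ = 0.5, n = 140 gives 1.96 × √(2 × 0.75 / 140) = 0.203, against 1.96 × √(2 / 140) = 0.234 unadjusted. Power uses the noncentral t distribution, with Mann-Whitney efficiency 3/π relative to the t test.

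**Normal data.** With 140 per arm and no use of V1, the half-width is 0.234 SD; power is 69% for Mann-Whitney and 71% for a t test.

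| ρ | ANCOVA variance cut | Half-width, ANCOVA | Half-width, change | Power, ANCOVA | Power, Mann-Whitney on change |
|---|---|---|---|---|---|
| 0.2 | 4% | 0.230 | 0.296 | 72% | 49% |
| 0.3 | 9% | 0.223 | 0.277 | 75% | 54% |
| 0.5 | 25% | 0.203 | 0.234 | 82% | 69% |
| 0.7 | 49% | 0.167 | 0.181 | 94% | 88% |

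At ρ = 0.1 the variance cut is only 1% and ANCOVA power is 71%. Low correlations are possible: section 7.1 requires RV overload with shock or hypotension, which may narrow the spread of V1 PASP, and section 3 expects treatment to normalise the pulmonary circulation.

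**Other sizes.** With 155 per arm the half-width falls from 0.223 SD to 0.218, 0.212, 0.193 and 0.159 SD across the four correlations. With 126 it falls from 0.247 SD to 0.242, 0.236, 0.214 and 0.176 SD.

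**Skewed data.** Simulated log-normal PASP, 140 per arm, with a shift of 0.3 SD and the correlation both on the log scale. Power for ρ = 0.2 / 0.3 / 0.5 / 0.7:

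| Log SD | Mann-Whitney | Plain ANCOVA | Log-scale ANCOVA |
|---|---|---|---|
| 0.5 | 68–69% | 67 / 68 / 76 / 89% | 72 / 74 / 82 / 94% |
| 0.8 | 68–69% | 59 / 59 / 66 / 79% | 73 / 74 / 82 / 94% |

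Under strong skew, plain ANCOVA is weaker than the planned test up to ρ = 0.5. The scale therefore has to be fixed in advance.

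**The case against.** The planned test is valid, so the precision argument concerns efficiency on one of six secondary outcomes, and its size rests on a correlation the documents do not give. At ρ = 0.2 the half-width hardly moves. The log-normal simulation also favours log-scale ANCOVA by construction, because normality holds exactly on that scale. In a deliberately heavy-tailed case (bivariate t with 3 degrees of freedom, 140 per arm, shift of 0.3 scale units), Mann-Whitney keeps about 50% power while ANCOVA has 35%, 37%, 43% and 56% at the four correlations. The non-inferiority margin is set for mortality only, and no claim of PASP similarity is planned. If means and SDs are reported, a reader can derive an unadjusted difference. A Hodges-Lehmann difference with its CI would close the estimate gap without a model.

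Much of this stands. The gain may be small, a rank test is defensible without distributional data, and the t case shows that ANCOVA can lose when tails are very heavy. That case is extreme, however, and is a reason to keep Mann-Whitney as a sensitivity analysis. A Hodges-Lehmann estimate would be a real improvement but would still ignore V1. The option of reporting only medians and IQRs leaves no assurance that a difference can be derived. None of these points supplies the missing pre-specified estimate or settles raw values against change.

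**Conclusion.** The concern holds, as an improvement the plan should make rather than a flaw in validity. The primary outcome, its sample size and the type I error are untouched. The missing between-arm estimate and the unstated choice of quantity are certain from the text. The precision gain depends on assumption: a variance cut of 4% to 49% for correlations of 0.2 to 0.7, and about 1% at 0.1. Under normality, with 140 per arm and a 0.3 SD effect, power rises from 69% to between 72% and 94%. This gain requires a suitable analysis scale; with strong skew on the raw scale, or very heavy tails, it can reverse.

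**What to change.** In section 18:

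1. State that V1 PASP is a covariate and not an outcome.
2. Analyse PASP at V2, V4 and V5 by ANCOVA with arm and V1 PASP, on a scale fixed in advance (for example log PASP, giving an adjusted ratio of geometric means). Report the adjusted between-arm estimate with its 95% CI at each visit, and keep Mann-Whitney as a sensitivity analysis. If one p value is to be quoted, name its visit beforehand.
3. State that the estimate applies to patients alive and measured at the visit, and show it beside deaths by arm.

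The cost is a paragraph and a few lines of R, with no new data. There are three downsides. The gain is small if the correlation is low. A rule is needed for patients without a measurable V1 PASP, for example overall-mean imputation of V1 with a missing-value indicator. A ratio of geometric means is also less direct to read than a difference in mm Hg.

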1. BACKGRAUND FOR THE TRIAL

Pulmonary embolism (PE) is a complex clinical problem. The prevalence of PE is high and reaches 30-40 people per 100 000 populations in Russia [1]. PE is one of the leading causes of death, morbidity and hospitalization in Europe [2]. It has been shown that in six EU countries (population about 450 million people), the mortality rate from PE is higher than from AIDS, breast cancer, prostate cancer and road traffic accidents combined, and is 11% of the entire population surveyed [2].

In the Russian Federation, mortality from PE is very high and ranges from 10-30%, depending on modern diagnostics and the use of adequate methods of treatment, primarily thrombolytic therapy.

The indication for thrombolytic therapy is massive PE, defined by size scales and risk stratification. Massive PE is defined in the presence of signs of shock or hypotension, which corresponds to III-V class PESI [1].

In accordance with European [1] and Russian [2] Guidelines for massive PE treatment, the following thrombolytic drugs are used:

- 1) streptokinase according to the standard scheme of administration for 12-24 hours or accelerated scheme for 2 hours;
- 2) urokinase according to the standard (12-24 hours) or accelerated schemes for 2 hours;
- 3) alteplase according to the standard scheme of 100 mg for 2 hours.

The recently completed PEITHO study used the «gold standard» thrombolytic therapy for acute ST-segment elevation myocardial infarction (STEMI) tenecteplase in patients with intermediate-risk PE with signs of right ventricular (RV) disease according to a single bolus administration at a dose of 30-50 mg, depending on body weight. Tenecteplase was shown to be highly effective, combined with a large number (6.3%) of hemorrhagic stroke, which did not allow tenecteplase to be included in the list of recommended thrombolytics for PE [3].

FRIDOM 1 study showed equal efficacy and safety of Fortelyzin®, 15 mg as a single bolus, regardless of body weight, compared with Metalyse® (tenecteplase), administered as a single bolus of 30-50 mg depending on body weight, in patients with STEMI. This study demonstrated the high efficacy of Fortelyzin® and its safety, the absence of major bleeding and hemorrhagic stroke in patients with STEMI complicated by cardiogenic shock [5, 6].

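### The 7-day mortality comparison makes no use of baseline PESI: a valid analysis that gives up a modest, undocumented amount of precision

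*Combined protocol and SAP*

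**What the plan says.** The primary endpoint in Section 11 is binary: "Primary efficacy outcome – death from any causes within 7 days". Section 18 is the only analysis text. For binary outcomes it states that a two-sided Fisher's "exact test will be used to compare categorical variables" and that "Odds ratios (ORs) will be estimated and presented with 95% CIs". It names no covariate, regression model or stratified test.

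PESI is a planned pre-treatment measurement. Section 8 lists "risk stratification to assess the prognosis according to the PESI classification" among the procedures for all patients before the trial. Table 5 has a row "PESI risk stratification" marked at V1 only. In Section 9 the Visit 1 list includes "PESI mortality stratification" ahead of randomisation and drug administration. Randomisation is by envelopes, and no stratification factor is stated. PESI is therefore collected and labelled prognostic, but used in neither the design nor the analysis.

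**The concern.** When a baseline variable predicts the outcome, adjusting for it removes the part of the outcome variance that it explains and corrects for chance differences between arms in that variable. The non-inferiority question in Section 17 is posed on the risk-difference scale with a 10-point margin, so a narrower interval for that difference has direct value. A clear severity difference between arms would also prompt requests for an adjusted analysis. If none is pre-specified, it will be post hoc and open to dispute. The data are already planned, so the cost of using them is small.

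**Working it through.** **Inputs from the documents.** Expected mortality 10% in both arms, margin 10 points, one-sided 2.5%, power 80%, 141 per arm, raised to 155 for dropout (Section 17). Average stay to discharge 14 days (Section 8).

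**Input not in the documents.** The strength of the PESI-mortality association. It is assumed here, as an AUC from 0.60 to 0.80.

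**1. The plan's own figure.** The Section 17 formula with p1 = p2 = 0.10, Δ = 0 and δ = 0.10 gives

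n = (1.960 + 0.842)² × (0.09 + 0.09) / 0.10² = 7.849 × 18 = 141.28 per arm.

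The plan states 141 (142 if rounded up). For dropout, 282 × 1.1 = 310.2, against 310 stated. The figure reproduces with no covariate, so the planned 80% power does not depend on adjustment.

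**2. Effect of adjustment.** Let R² be the share of the variance of 7-day death explained by PESI. The variance of the risk difference is multiplied by (1 − R²), so

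SE = √[2p(1 − p)(1 − R²)/n], and power = Φ(0.10/SE − 1.96).

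Unadjusted: SE = √(0.18/141) = 0.0357, half-width 1.96 × 0.0357 = 7.0 points, power 79.9%.

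For a logistic risk model with a normally distributed score, R² = Var(E[Y given score]) / [p(1 − p)]. At p = 0.10 and n = 141 per arm:

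| Assumed AUC | R² | Power | 95% CI half-width (points) | Equivalent extra patients per arm, 141/(1 − R²) − 141 |
|---|---|---|---|---|
| none | 0 | 79.9% | 7.0 | 0 |
| 0.60 | 1.2% | 80.4% | 7.0 | 2 |
| 0.65 | 2.8% | 81.0% | 6.9 | 4 |
| 0.70 | 5.4% | 82.1% | 6.8 | 8 |
| 0.75 | 9.2% | 83.6% | 6.7 | 14 |
| 0.80 | 14.6% | 85.7% | 6.5 | 24 |

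**3. Check by simulation.** Logistic standardisation at 141 per arm (3,000 replicates per scenario) gave adjusted-to-unadjusted variance ratios of 0.98, 0.92 and 0.81 at AUCs of about 0.63, 0.75 and 0.83. The ratio was 1.01 for a covariate with no prognostic value. The formula holds at this sample size, and a useless covariate costs almost nothing.

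**4. Where in the range.** Section 1 says of massive PE, defined by shock or hypotension, "which corresponds to III-V class PESI", and hypotension or shock is an inclusion criterion. A restricted range of severity tends to lower discrimination, so the upper rows are less likely.

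**5. Lower event rate.** The 10% in Section 17 is in-hospital mortality, while the endpoint stops at day 7. With assumed 7-day mortality at an AUC of 0.70 and 141 per arm:

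- 7%: R² = 4.1%, power 90.8% to 91.9%.
- 5%: R² = 3.1%, power 97.1% to 97.5%.

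**6. Chance imbalance.** The shift in the mortality difference that chance PESI imbalance exceeds in 5% of trials is 1.96 × √[2p(1 − p)R²/n]. At 10% mortality this is 1.6 points for an AUC of 0.70 and 2.1 for 0.75. The 7.0-point half-width of the unadjusted interval already contains this variation.

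**7. Events available.** At 10% mortality, 282 × 0.10 = 28 to 310 × 0.10 = 31 deaths. At 5% to 7%, 282 × 0.05 = 14 to 282 × 0.07 = 20 deaths.

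**The case against.** The strongest reply is that nothing here is wrong. An unadjusted comparison of randomised arms is valid, its interval allows for chance imbalance, and 141 per arm was derived for exactly that comparison. This stands in full. A reader might infer that the planned analysis is biased or that the trial is underpowered without PESI. The documents support neither.

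Second, the size rests on an AUC that appears nowhere in the documents. A reader might take 82% to 84% power, or 8 to 14 patients per arm, as the expected gain. Those figures belong to AUCs of 0.70 to 0.75 at 10% mortality only, and the plan's own description of the population points lower.

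Third, Section 18 contains no risk-difference interval to be narrowed. Fisher's test at p below 0.05 and an odds ratio do not test non-inferiority against the 10-point margin. This also stands: that gap is the more serious one and has to be closed first. The power figures above compare two risk-difference analyses, neither of which is written in the plan.

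Fourth, the precision is not entirely free. The documents speak of PESI as a classification, a stratification and a class, and never say that a numeric score is recorded. They give no rule for missing PESI, although patients with shock or cardiac arrest are eligible.

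A reader might also infer that the open-label design makes PESI imbalance more of a threat. Open-label treatment does not cause chance baseline imbalance, and the documents give no support for that link.

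What survives is that a pre-treatment variable the protocol itself treats as prognostic goes unused, and that using it costs little.

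**Conclusion.** The point holds as a cheap improvement, not as a correction of an error. At 10% mortality and 141 per arm, PESI adjustment would raise power from 79.9% to about 80.4% to 83.6% (AUC 0.60 to 0.75) and reduce the half-width from 7.0 points to between 7.0 and 6.7. The lower end is more likely. At 5% to 7% mortality and an AUC of 0.70, the gain is about 1 power point or less (0.4 to 1.1).

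These sizes rest on three assumptions: the AUC, a roughly normal risk score, and a primary analysis based on the risk difference. None of the three is stated in the documents. The further benefit, a pre-specified answer if severity happens to differ between arms, does not depend on the exact AUC, though it too is limited if PESI is weakly prognostic in this population.

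**What to change.** Amend Section 18 before mortality by arm is examined:

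- **Primary estimate.** When the primary analysis is rewritten as a risk-difference confidence interval compared with the 10-point margin, base it on a logistic model with arm and V1 PESI, standardised over all patients to a marginal risk difference, with a robust or bootstrap 95% CI. A PESI-adjusted odds ratio would not serve, because it is a conditional measure on a different scale from the margin.
- **Form of PESI.** Use the numeric score if the CRF records it, and the class otherwise. State which.
- **Missing PESI.** State one simple rule that keeps every randomised patient, for example the median score (or most frequent class) over both arms combined.
- **Sensitivity analysis.** Report the unadjusted risk difference with its 95% CI.

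The sample size need not change. The cost is a few lines of text, slightly more analysis work and possibly a CRF clarification that the numeric score is recorded. About 28 to 31 expected deaths support one covariate. With only 14 to 20 the model should stay at that single term. No visit, procedure or patient is added.

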The results of the FRIDOM1 study showed that the timing of PCI after thrombolysis does not affect the thrombolysis safety.

FRIDOM1 trial confirmed the «non-inferiority» hypothesis. The results of the efficacy and safety endpoints showed that Fortelyzin® administered as a single bolus in a dose of 15 mg regardless of body weight is non-inferiority to Metalyse® administered as a bolus at a dose of 30-50 mg depending on body weight in patients with STEMI no later than 12 hours from the onset of the disease. This trial has demonstrated a similar safety profile.

The Ministry of Health of the Russian Federation conducted an examination of FRIDOM1 trial results and approved updated Fortelyzin® instructions, allowing its

single bolus administration at a dose of 15 mg in patients with STEMI no more than 12 h symptoms onset, including in patients with cardiogenic shock.

Fortelyzin® efficacy and safety monitoring

Continuous monitoring of the Fortelyzin® efficacy and safety is carried out and covers 4123 STEMI patients for the period from June 2013 to March 2015.

The average age of STEMI patients who received Fortelyzin® was 64 years, 610 people were older than 75 years old (72% of the total number of patients were male). According to the localization of myocardial infarction, the patients were distributed almost equally (Table 2).

Table 2. Main characteristics of patients treated with Fortelyzin®

Number of patients	Sex, m/f	Average age, Min-max (years old)	Number of patients > 75 years old	Localization of infarction		Average door-to-needle time Min-max (min)
				anterior	posterior	
4123	2981/1142	64 32–93	610 (15%)	2300	1823	206 40–720

The time from the STEMI symptoms onset to Fortelyzin® administration was 206 minutes. Signs of myocardial reperfusion, according to ECG data, by the 90th minute with a non-invasive strategy were observed in 2542 of 3139 patients (81%), with a pharmacoinvasive strategy – in 826 of 984 patients (83%).

With a pharmacoinvasive strategy, according to coronary angiography, coronary blood flow restoration according to TIMI 3 criteria was observed in 403 of 984 patients (41%), according to TIMI 2 criterion – in 305 patients (31%), in total, according to the sum of TIMI 2-3 – in 708 of 984 patients (72%).

Hemorrhagic stroke occurred in 9 (0,3%) patients with the non-invasive strategy and in 3 patients (0,3%) with the pharmacoinvasive strategy.

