12. SAFETY ENDPOINTS

- Safety outcomes – ischemic and hemorrhagic strokes within 7 days;
- Safety outcomes – bleedings BARC type 3 and 5;
- number and severity of SAEs and AEs in organs and systems.

Adverse events

Adverse event (AE) is an unfavorable medical occurrence in a patient administered a pharmaceutical product, which may not have a causal relationship with its use. Thus, an AE can be any adverse symptom (including deviation of the laboratory value from the norm), a complaint, or a disease, the time of occurrence of which does not exclude a causal relationship with the use of the medicinal product, regardless of the presence or absence of such communication.

Information about AEs should be collected at each visit by interviewing the patient, as well as during physical examination and evaluation of laboratory and instrumental data. All AEs that occur during the trial should be evaluated and documented.

When registering an adverse event, the following information should be reflected, if possible:

- the exact time of AE occurrence и разрешения

- the nature of the AE
- severity (mild, moderate, severe)
- causal relationship with the study drug
- whether the AE is serious
- actions taken (whether AE required any therapeutic measures)
- outcome

AEs Grading:

- **Mild:** the presence of signs or symptoms that do not affect daily activities.
- **Moderate:** AE has sufficient intensity to interfere with daily activities.
- **Severe:** inability to work or perform daily activities.

The connection between the development of AE and the use of the study drug is determined by the WHO scale:

- ***definitely related:*** Clinical manifestations of AE, laboratory findings deviations that occur during the period of drug administration, cannot be explained by the presence of existing diseases and the influence of other factors. Manifestations of AE regress after the drug discontinuation and occur again after repeated administration.
- ***Probable.*** Clinical manifestations of AE, laboratory findings deviations are associated with the time of drug administration, unlikely to be related to concomitant diseases or other factors, and which regress with drug withdrawal. Response to the drug re-challenge is unknown.

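### Stroke and BARC 3/5 bleeding have no planned risk difference, and Section 18 does not say how the odds ratio is handled when an arm has no events

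*Combined protocol and SAP*

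**What the plan says.** Safety is one of the two objectives in Section 6. Section 12 names two specific safety outcomes, "Safety outcomes – ischemic and hemorrhagic strokes within 7 days" and "Safety outcomes – bleedings BARC type 3 and 5", followed by adverse events in general.

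Section 18 has no separate safety analysis. Its rules for categorical data apply to efficacy and safety alike:
- Within each arm: "Categorical variables will be presented as n (%) and corresponding 95% Clopper-Pearson confidence intervals (CI".
- Test: "the two-sided Fisher's exact test will be used to compare categorical variables".
- Effect measure: "Odds ratios (ORs) will be estimated and presented with 95% CIs".
- Significance: "Outcomes will be considered as statistically significant if the p value will less than 0,05".

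It does not mention a risk difference, a method for the odds-ratio interval, or a rule for a zero cell. Section 8 fixes the arm size: patients are "randomized using the «envelope method» into two equal groups of 155 patients each". No expected stroke or BARC 3/5 rate in massive PE appears anywhere.

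**The concern.** The odds ratio is the only between-arm effect measure in the plan. If one arm has no events its point estimate is 0 or infinite; if neither has any, it does not exist. A standard large-sample (Wald) interval fails in both cases. The planned arm-wise Clopper-Pearson intervals remain finite at zero events, but two separate intervals are not an interval for the difference.

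The protocol's own experience with the study drug in STEMI shows how rare such events can be. In the monitoring series, "Hemorrhagic stroke occurred in 9 (0,3%) patients with the non-invasive strategy", and the randomized STEMI trial against tenecteplase had no intracranial hemorrhage in 191 patients per arm. With similar rates here, the between-arm safety result could reduce to a degenerate odds ratio and a non-significant p-value. Neither tells a reader how large an excess the data exclude.

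**Working it through.** **Arm size.** The plan gives no figure for the safety comparison; only its n bears on it. Section 17 sizes the trial on mortality: (1.960 + 0.842)² × [0.1×0.9 + 0.1×0.9] / 0.10² = 141.3, against 141 stated. Then 141 × 1.1 = 155.1, against 155 stated. I use n = 155 per arm.

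**Rates available in the documents.**
- Hemorrhagic stroke, STEMI monitoring series (Section 2): (9 + 3)/(3139 + 984) = 12/4123 = 0.29%.
- Major bleeding, randomized STEMI trial (Section 2, Table 1): 0.5% per arm.
- Bleeding requiring transfusion, monitoring series (Section 2, Tables 3 and 4): 0.7%.
- Blood transfusion, randomized STEMI trial (Table 1): 3.7% on the study drug, 10.5% on the comparator.
- Hemorrhagic stroke on tenecteplase in intermediate-risk PE, as Section 1 states it: 6.3%.

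The 1%, 2% and 3% rows below are my assumptions to fill the range.

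**Chance of an empty arm.** With the same rate p in both arms, q = (1 − p)^155 is the chance that one arm has no events. At least one empty arm: 1 − (1 − q)². Both empty: q².

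| Rate p | q | At least one arm empty | Both empty |
|---|---|---|---|
| 0.29% | 0.637 | 87% | 40% |
| 0.5% | 0.460 | 71% | 21% |
| 0.7% | 0.337 | 56% | 11% |
| 1% | 0.211 | 38% | 4.4% |
| 2% | 0.044 | 8.5% | 0.2% |
| 3% | 0.009 | 1.8% | <0.01% |
| 3.7% | 0.003 | 0.6% | <0.01% |
| 6.3% | <0.001 | 0.01% | <0.01% |

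**What each measure gives with a zero cell** (events on Fortelyzin versus Actilyse, 155 per arm). The odds ratio is the conditional estimate with an exact 95% interval, a method the plan does not name. The risk difference has a Newcombe 95% interval.

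| Events | Fisher p | Odds ratio (exact interval) | Risk difference, points |
|---|---|---|---|
| 0 vs 0 | 1.0 | undefined (0 to ∞) | 0.0 (−2.4 to +2.4) |
| 0 vs 1 | 1.0 | 0 (0 to 39.0) | −0.6 (−3.6 to +1.8) |
| 0 vs 3 | 0.25 | 0 (0 to 2.41) | −1.9 (−5.5 to +0.8) |
| 3 vs 0 | 0.25 | ∞ (0.41 to ∞) | +1.9 (−0.8 to +5.5) |
| 5 vs 0 | 0.060 | ∞ (0.93 to ∞) | +3.2 (+0.2 to +7.3) |

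The 0 versus 0 limit follows from the Wilson upper limit for 0/155: z²/(n + z²) = 3.84/158.84 = 2.4%. The Clopper-Pearson upper limit for one such arm is 1 − 0.025^(1/155) = 2.35%.

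**What the 0.05 rule can see.** For k events against none, Fisher p = 2 × C(155,k)/C(310,k): 0.060 at k = 5 and 0.030 at k = 6. Six against none is the smallest such split below 0.05. By enumeration, Fisher power is 10% for 1% vs 3%, 19% for 2% vs 5% and 16% for 3% vs 6%. It reaches 85% only for a contrast as extreme as 0.3% vs 6.3%.

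**The case against.** A reader might infer more than the documents support, in five ways.

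1. *That the odds ratio will usually be degenerate.* The rates that produce 56–87% are all low STEMI figures. The same documents cite 3.7% and 10.5% transfusion in the randomized STEMI trial and 6.3% hemorrhagic stroke in a PE population, where an empty arm is very unlikely. The stroke outcome also includes ischemic stroke, so 0.29% understates it if both types are counted together. The documents do not equate transfusion with BARC 3/5, and they give no rate for massive PE. This objection stands: the problem is conditional on the rate.

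2. *That no usable between-arm estimate exists.* With events in one arm only, an exact odds-ratio interval keeps one finite bound, and counts with Clopper-Pearson intervals are planned for each arm. That stands too. What remains is that no exact method is specified, 0 versus 0 yields nothing, and no interval for the difference is planned.

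3. *That the plan treats p≥0.05 as equal safety.* It does not. Section 18 only says when a result is called significant. Section 12 bases safety assessment on the number and severity of events, Section 19 provides committee reviews at 25%, 50% and 75% of enrollment, and Section 20 calls for discussion of adverse events. A caution is still worthwhile, because Section 2 concludes similar safety in the randomized STEMI trial from a table in which most rows have p>0.99 on 0 or 1 events per arm.

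4. *That the remedy cures low power.* It does not. Power reflects an n chosen for mortality, and a different effect measure adds no information. Nor does the 5 versus 0 example show that Fisher's test is wrong; there an approximate interval and an exact test disagree near the boundary.

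5. *That the rare-event argument covers all serious adverse events.* These include deaths, expected at 10% in Section 17, and hemodynamic collapse. The argument does not extend to them.

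**Conclusion.** The concern holds in a limited form. Section 18 leaves the between-arm safety comparison for stroke and BARC 3/5 bleeding to an odds ratio with no zero-cell rule and no named interval method, plus a low-power significance rule. At rates of 0.29% to 0.7% in both arms of 155, at least one arm is empty with probability 87% down to 56%, and both with probability 40% down to 11%. At 3% or more the first figure is under 2%, and the odds ratio is normally estimable. These figures assume equal true rates, full arms of 155 and independent patients. Because the true rate is not given, a measure that is finite across the whole range is the better choice. This is an inexpensive improvement in reporting; it is not a flaw that invalidates the safety analysis.

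**What to change.** In Section 18, for stroke by day 7 and BARC type 3 or 5 bleeding only:
- Report the risk difference with a 95% Newcombe or Miettinen-Nurminen interval as the main between-arm safety result.
- Give the odds ratio only when both arms have events, or give it with a named exact interval.
- State that p≥0.05 is not evidence of similar safety, and that the interval shows what excess is excluded. With no events in either arm, that is an excess above about 2.4 points.

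Fisher p-values can stay. The cost is a few sentences, a few lines of extra analysis and a more cautious safety statement. No new data or change in sample size is needed.
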